3.2 Data and sample handling and analysis

We will not be using any paper records. Demographic, contact and questionnaire data will be collected using bespoke software (Microsoft ODK) on tablets and automatically uploaded to a secure, password protected Imperial server. The physiological measurements are automatically stored on their linked laptops and will be regularly transferred to the same server. We will retain records of all participants sufficient to link their crfs, questionnaires, measurements and samples; and all original signed informed consent forms.

Periodically, through the course of the prospective study, we will estimate the associations between semi-quantitative estimates of Grenfell exposure and incident respiratory, cardiovascular and cancer outcomes obtained through data linkage, after controlling for potentially confounding exposures such as other firesmoke exposures and smoking. Similarly, we will examine associations between the physiological measurements made at survey and subsequent incidents of cardiac and respiratory disease. Our sample size is, necessarily, constrained and because of the unique nature of the Grenfell fire we cannot make meaningful estimates of the statistical power of the prospective study.

We can, however, estimate the power of relating exposure at the Grenfell fire to the physiological measurements made at the baseline survey. There will be, we anticipate, sufficient variation between firefighters in their exposures at Grenfell to allow 'internal' comparisons of the above measures between exposure groups but we will include also an unexposed reference group of 'eligible but unexposed' LFB firefighters.

London

In this respect, our primary hypothesis is that intense exposure at Grenfell will have given rise to deficits in small airways function as measured through impulse oscillometry. Measurements in almost 500 Australian firefighters (*Schermer T et al. Respirology (2010) 15, 975–985*) suggest that R5 distributes Normally with a mean of 0.27kPa/L/s and a standard deviation of 0.08. On the assumption that there were 100 heavily exposed firefighters and 900 with lesser exposures and that 80% of each group participate in the survey, we will have, on internal comparison, 90% power to detect a minimum between-group difference of 0.027kPa/L/s (α =0.05). This estimate depends on their being an equal distribution of potential confounders between the two groups which we think is a reasonable

assumption. There is not yet an established minimal clinically important difference for R5 (or other oscillometry values) but it will almost certainly be >0.02; our intent, however, would be simply to compare values across exposure strata to establish cause/effect.

The primary statistical analysis will be of the relationship between R5 and 'Grenfell exposure', an independent, ordinal variable with several levels including nil. Secondary analyses will be of other, continuous and categorical measures of respiratory function and symptoms and of arterial stiffness. Univariable analyses will be through ANOVA or Kruskall Wallis (as appropriate) with a non-parametric test of trend, an extension of the Wilcoxon rank-sum test. We will subsequently undertake linear regression analyses adjusting for non-Grenfell firesmoke exposures (likely a continuous measure) and other potential confounders including age, sex, ethnicity, BMI, smoking and other non-firefighting occupational exposures (Yes/No).

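### At a two-sided alpha of 0.05, the 80 v 720 participants assumed in Protocol section 3.2 give 90% power for about 0.031 kPa/L/s, not the stated 0.027, and the sidedness is not stated

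*Protocol*

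**What the plan says.** Protocol section 3.2 says that power for the prospective study cannot be meaningfully estimated. It then gives one power statement, for the baseline survey, in support of the primary hypothesis about R5. The inputs are:

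- **Distribution of R5:** "R5 distributes Normally with a mean of 0.27kPa/L/s and a standard deviation of 0.08", taken from a survey of Australian firefighters.
- **Group sizes and participation:** "100 heavily exposed firefighters and 900 with lesser exposures and that 80% of each group participate in the survey".
- **Result:** "we will have, on internal comparison, 90% power to detect a minimum between-group difference of 0.027kPa/L/s", at an alpha of 0.05 with no sidedness attached.

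The hypothesis is worded with a direction: "our primary hypothesis is that intense exposure at Grenfell will have given rise to deficits in small airways function". The tests follow in the same section: "Univariable analyses will be through ANOVA or Kruskall Wallis (as appropriate) with a non-parametric test of trend". Adjusted linear regression comes after that. No one-sided test is mentioned anywhere.

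**The concern.** The sentence gives everything needed to recompute its result except the sidedness of alpha. Under the usual two-sided reading, the stated participation and the stated result do not agree. The printed difference is smaller than 80 v 720 participants can detect with 90% power.

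This is the only power statement in the protocol and it concerns the primary hypothesis. If it is too favourable, a reader will think the survey more sensitive than it is. Under the two-sided reading, the chance of missing a true difference of 0.027 is about 18%, not 10%. The number of attenders is fixed, so the survey cannot simply be enlarged. What can be corrected is the statement of its sensitivity.

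**Working it through.** **Inputs, all from Protocol section 3.2.** SD 0.08. Groups of 100 and 900. Participation 80% in each, so 0.8 × 100 = 80 and 0.8 × 900 = 720. Alpha 0.05. Power 90%. Sidedness is not given, so both are tried.

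**Formulas** (comparison of two means, normal approximation):

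- SE = SD × √(1/n₁ + 1/n₂)
- Detectable difference = (z for alpha + z for power) × SE
- Power at difference d = Φ(d/SE − z for alpha)

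The z values are 1.960 (two-sided 0.05), 1.645 (one-sided 0.05) and 1.2816 (90% power).

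**Step 1: which inputs come close to the printed figure?**

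100 v 900, two-sided:
- SE = 0.08 × √(1/100 + 1/900) = 0.08 × 0.10541 = 0.00843
- Detectable difference = 3.2415 × 0.00843 = 0.0273
- Power at 0.027 = 89.3%

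80 v 720, one-sided:
- SE = 0.08 × √(1/80 + 1/720) = 0.08 × 0.11785 = 0.00943
- Detectable difference = (1.645 + 1.2816) × 0.00943 = 0.0276
- Power at 0.027 = 88.9%

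Either is within about one percentage point of the stated 90%. Only the first rounds to 0.027.

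**Step 2: the stated participants with a two-sided alpha.**

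- Detectable difference = 3.2415 × 0.00943 = 0.0306
- Power at 0.027 = Φ(0.027/0.00943 − 1.960) = Φ(0.904) = 81.7%
- The noncentral t gives 81.6%.

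| Participants | Alpha 0.05 | Detectable at 90% power (kPa/L/s) | Power at 0.027 |
|---|---|---|---|
| 80 v 720 | two-sided | 0.0306 | 81.7% |
| 80 v 720 | one-sided | 0.0276 | 88.9% |
| 100 v 900 | two-sided | 0.0273 | 89.3% |
| 100 v 900 | one-sided | 0.0247 | 94.0% |

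**Step 3: can rounding of the SD explain the gap?** An SD printed as 0.08 could lie between 0.075 and 0.085. To detect 0.027 with 90% power at 80 v 720, the SD would have to be 0.0707 two-sided, which is outside that range, or 0.0783 one-sided, which is inside it. At the favourable end (SD 0.075), the two-sided detectable difference is still 0.0287 and power at 0.027 is 86.3%. Rounding therefore cannot rescue the two-sided reading, but it could account for the one-sided one.

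**Step 4: a rank test.** With an efficiency of 3/π relative to the t-test, two-sided power at 0.027 with 80 v 720 is about 80%. The non-parametric option in the plan does not close the gap.

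**The case against.** The strongest reply is that alpha may have been one-sided. The hypothesis speaks of deficits, exposure is ordinal, and a trend test can be run in one direction. A one-sided calculation with participation applied gives 88.9% power at 0.027, close to the claim. The difference of 0.027 is also exactly 10% of the stated mean of 0.27. It may have been a chosen target, in which case its third decimal says nothing about how it was reached.

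Part of this stands. A reader might infer that the calculation left out the 80% participation, because 100 v 900 two-sided gives 0.0273. The protocol does not establish that. The one-sided reading fits almost as well, and the participation rate stands in the very sentence that gives the result.

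It does not make the printed figure right as it stands. No one-sided test is declared. An unqualified 0.05 is normally read as two-sided, ANOVA and Kruskal-Wallis have no direction, and the regression is given none. An expected direction of effect does not define a one-sided rejection region. If one-sided was meant, the text still has to say so.

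A second stronger reading is that the survey is underpowered for a clinically important difference, since the protocol says of that difference "but it will almost certainly be >0.02". Two-sided power at 0.02 with 80 v 720 is indeed only about 56%. But the protocol gives 0.02 as a lower bound, says no value is established, claims no power there, and describes its aim as comparing exposure strata. That is not a second error.

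It is also fair to say that the correction changes no recruitment, test or analysis. What a null result excludes will depend on the observed estimate and its interval.

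**Conclusion.** The point holds conditionally. If alpha is two-sided, the stated 90% power at 0.027 kPa/L/s does not follow from section 3.2's own inputs. The detectable difference is about 0.031 (0.0306/0.027 = 1.13, so 13% larger), and power at 0.027 is about 82%, a shortfall of about 8 percentage points. If alpha is one-sided, the figure is nearly right (0.0276, which rounds to 0.028), but the protocol omits the condition that it depends on.

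This rests on the protocol's own SD of 0.08, its 80% participation, its two-group simplification and its assumption that confounders are balanced. The two-sided reading is a judgement from convention and from the tests named. Omitted participation is a plausible cause of the discrepancy and not a demonstrated one.

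Severity is moderate. The only power statement for the primary hypothesis is too favourable under its ordinary reading, but nothing in the conduct of the study depends on it.

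**What to change.** In Protocol section 3.2, replace the power sentence with wording to this effect: *with 80 heavily and 720 lesser exposed participants, the survey has 90% power (two-sided alpha 0.05) to detect a difference in R5 of 0.031 kPa/L/s; power at 0.027 is about 82%.*

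If a one-sided test was intended, say so, justify it, give the detectable difference as 0.028, and make the planned tests agree with it.

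The cost is one sentence. No further recruitment or change of analysis is needed, and the only downside is a slightly less favourable figure.

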both were undertaken over 30 years ago; neither showed any adverse effects attributable to firefighting.

Studies such as these are designed to reflect cumulative exposure(s) to repeated, relatively lowintensity events and their findings may not be applicable to those who fought the Grenfell fire. In a manner similar to that of the Grenfell firefighters, rescue and other workers at the World Trade Center (WTC) in 2001 experienced an abrupt and substantial, increase in exposure. While comparisons must be limited by the very different natures of the exposures (respectively, fire smoke vs dust of high alkalinity), increased rates of respiratory symptoms, airflow obstruction and bronchial hyperreactivity, and a stepwise fall in lung function, have been reported in WTC workers (13, 14). There has been only one other study of firefighters exposed to non-routine firefighting. Twenty (of 175) firefighters who extinguished an unusually intense chemical fire in Houston were followed over 18 months, during which they experienced, on average, declines in FEV1 and FVC of 122ml and 62ml respectively (15); the study is limited not only by its size but also by the lack of any pre-event spirometry.

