1.2 Study Rationale

The Grenfell firefighter population offers a rare opportunity to study the effects of intense fire smoke inhalation on a range of mid- and long-term outcomes. The population is readily defined and enumerated and can, through contemporary records, be subdivided into descending categories of exposure at the Grenfell fire, allowing internal comparisons in the assessment of cause and effect.

London

Importantly, and uniquely, detailed records held by the LFB will provide an objective, semiquantitative estimate of professional exposure to fire smoke before and after the Grenfell incident; moreover, periodic, three-yearly health surveillance, undertaken as a condition of active employment at LFB, will provide pre-incident information on lung health including spirometry.

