3. STUDY DESIGN AND METHODS

3.1 Design and procedures

On our behalf, to satisfy the requirements of GDRP, LFB will identify the names and contact details of all firefighters who directly attended the Grenfell Tower fire in June 2017; every effort will be made to include those who have left service since the fire, estimated to number no more than a dozen. In addition we will ask LFB to identify a random sample (n=100) of firefighters from stations close to Grenfell Tower who would have been eligible to attend the fire but did not do so because of annual leave.

Each of the above will be invited, by the Brigade, to contact us with regard to enrolling in a long-term, prospective study.

Those who do so make contact will be invited to:

London

- 1. provide consent to, and the necessary information (name, date of birth, sex, NHS number and contact details) for prospective linkage to national registers including those of mortality, cancer incidence, hospital admission and A/E attendance, and GP consultations.
- provide consent for their individual histories of employment and firesmoke exposure at and other than Grenfell to be released to Imperial College by LFB, and for this information to be periodically updated; and to provider similar consent for access to their past and subsequent lung function measurements made in the normal course of their employment by LFB.
- 3. participate in an independent and confidential survey of (cardio)respiratory health, to take place in the clinical research facility of Royal Brompton hospital in London. For those who choose to take part, we will collect the consents and information in 1 and 2 above at the time of survey; for the remainder we will communicate by post, and include the questionnaire outlined below.

For the baseline survey, we have elected to use investigative methods which are well-established and which can be completed fairly rapidly; moreover, our tests need to be minimally invasive since it will be essential that participation in the project will not impede an immediate return to active work.

The information we propose to collect is listed below:

A. Demographics and confounding exposures

Through self-completed questionnaire, the collection of some simple demographic and lifestyle information, to include:

- age/sex
- duration of employment as a firefighter
- smoking: detailed (pack years; age of starting/quitting)
- other, relevant occupational and non-occupational exposures

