- other relevant ill-health and medications

Participants will be invited to complete the questionnaire using a web-based tool designed specifically for this study.

B. Respiratory health assessment

• a respiratory symptoms questionnaire incorporating standardised questions that focus on breathlessness and cough, modified from the Dyspnoea 12 instrument; to include also an enquiry into prior respiratory health, diagnoses and relevant treatments

• small airways function; we will measure resistance of the respiratory tract at 5 and 20 Hz (R5 and R20) using impulse oscillometry (Master Screen Spirometry-IOS System, Jaeger, Germany). Participants will be seated and will undertake a minimum of three trials, each lasting 30s, during tidal breathing while firmly supporting their cheeks with their hands.

• spirometry: following oscillometry and using a standard, electronic spirometer (Vitalograph, Buckingham, UK) in accordance with internationally accepted guidelines (29), we will measure FEV₁, FVC and small airway flows.

• bronchodilator reversibility: the above measurements of lung function will be repeated 15 minutes after the administration of a bronchodilator (400µg inhaled salbutamol through a 'spacer' device).

C. Cardiovascular health assessment

• arterial stiffness: we will measure pulse wave velocity and augmentation index using a Vicorder (Skidmore Medical, Bristol, UK). Central aortic pulse wave velocity will be defined as the

London

ratio of pulse wave transit time and distance between the carotid and femoral arteries and augmentation index by the enhancement of central aortic pressure by a reflected pulse wave.

D. Biosampling: we do not plan to undertake analyses of these samples within this project but will retain them for future work to examine – at a later date - epigenetic and other 'omic changes

- a venous blood sample (serum and plasma)
- a urine sample

After collection and processing, the samples will be stored in a dedicated freezer at -80°C.

Firesmoke exposure assessment:

Grenfell

• we will, with experts from LFB and with the use of contemporaneous records, develop a tool which will provide semi-quantitative estimates, for all consenting cohort members, of individual exposure to fire smoke during the Grenfell fire.

pre- and post-Grenfell

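### The survey analysis in section 3.2 names no use for the pre-fire LFB spirometry, so FEV1 and FVC are compared across non-randomised exposure strata without it

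*Protocol*

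**What the plan says.** Three places in the Protocol treat pre-fire spirometry as valuable.

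- Section 1.1, on the small chemical-fire study: "the study is limited not only by its size but also by the lack of any pre-event spirometry".
- Section 1.2, on this cohort: "periodic, three-yearly health surveillance, undertaken as a condition of active employment at LFB, will provide pre-incident information on lung health including spirometry".
- Section 3.1 asks participants to consent to "access to their past and subsequent lung function measurements made in the normal course of their employment by LFB".

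Section 3.1 also has the survey measure FEV1, FVC "and small airway flows". Section 3.2 makes R5 by impulse oscillometry the primary outcome, with the other respiratory measures secondary. Each is related to ordinal Grenfell exposure, first by ANOVA or Kruskal-Wallis with a trend test. Then: "We will subsequently undertake linear regression analyses adjusting for non-Grenfell firesmoke exposures (likely a continuous measure) and other potential confounders". The potential confounders named are age, sex, ethnicity, BMI, smoking and a yes/no item for other occupational exposures. Section 3.2 gives the LFB spirometry no role as covariate, change score, serial outcome or balance check.

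**The concern.** Exposure at Grenfell was not randomised, yet section 3.2 intends the comparison across exposure strata to support a causal conclusion. Its power statement assumes that confounders are equally distributed between the heavily and less exposed groups. Pre-fire spirometry is the only objective measurement described in the protocol that could show whether the strata already differed in lung function. It predates the exposure, so adjusting for it does not remove part of the effect being sought.

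If the listed model is fitted as written, two things are lost for FEV1 and FVC. Any pre-fire difference between strata that the other covariates do not explain stays in the exposure contrast, and variation between people that the pre-fire value would explain stays in the error term. The protocol names the same gap as a limitation of the earlier study.

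**Working it through.** **Coverage of the text.** Section 3.2 contains two sets of analyses.

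| Analysis in 3.2 | Outcome | Pre-fire LFB spirometry used? |
|---|---|---|
| Prospective, Grenfell exposure | incident disease by linkage | not mentioned |
| Prospective, survey physiology | later cardiac and respiratory disease | not mentioned |
| Survey, primary | R5 | not mentioned; no pre-fire oscillometry described |
| Survey, secondary | FEV1, FVC, other measures | not mentioned |

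**The plan's own figure.** The only power statement is for R5: SD 0.08, difference 0.027 kPa/L/s, 80 v 720 participants (80% of 100 and of 900), alpha 0.05, 90% power. With 80 v 720 it reproduces as a one-sided test (0.889) but not as a two-sided one (0.817). That is a separate matter. The protocol gives no figure for FEV1 or FVC, so what follows rests on stated assumptions.

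**Precision.** Adding a covariate whose correlation with the outcome is r, after the covariates already in the model, multiplies the standard error (SE) of the exposure contrast by sqrt(1 - r²). This takes the pre-fire value to be roughly balanced across strata; imbalance would reduce the gain.

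The r that counts is the partial correlation, because the planned model already contains age, sex, ethnicity, BMI and smoking. For illustration, assume those covariates explain a share R² of the variance at both times through the same component. Then partial r = (raw r - R²)/(1 - R²).

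| Raw r (assumed) | R² (assumed) | Partial r | SE factor | SE cut |
|---|---|---|---|---|
| 0.6 | 0.3 | 0.3/0.7 = 0.429 | 0.903 | 10% |
| 0.9 | 0.3 | 0.6/0.7 = 0.857 | 0.515 | 48% |
| 0.6 | 0.5 | 0.1/0.5 = 0.200 | 0.980 | 2% |
| 0.9 | 0.5 | 0.4/0.5 = 0.800 | 0.600 | 40% |

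**Detectable difference.** For 80 v 720, two-sided alpha 0.05 and 90% power, the planned model can detect sqrt(1/80 + 1/720) × (1.960 + 1.282) = 0.1179 × 3.242 = 0.382 residual SD. With the pre-fire value added this becomes 0.382 × 0.980 = 0.374 SD at partial r 0.2, and 0.382 × 0.515 = 0.197 SD at partial r 0.857.

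**Confounding.** If two strata differ by d residual SDs in pre-fire lung function, and the SDs before and after are equal, adjustment subtracts r × d from the post-fire contrast. Over the range above that is 20% to 86% of any pre-fire gap. Because r is below 1, a lasting gap is only partly removed when a single, imperfect and possibly years-old measurement is used.

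**The case against.** The strongest reply is that silence is not exclusion. The covariate list is introduced as examples, so it is open. The secondary analyses are described broadly, consent for the LFB data is sought, and a statistical analysis plan, which is not at hand, could add a baseline covariate or a model of serial values. This stands to the extent that a reader should not infer that pre-fire spirometry has been ruled out; the text supports only that no use is named. It does not dispose of the point. The protocol chooses to state its model and name its covariates, and it omits the one its own rationale argues for.

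Other inferences are tempting but not supported:

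- **That the primary analysis lacks an available baseline.** The LFB records are described as lung function and spirometry, with no pre-fire oscillometry. Section 1.1 also notes that spirometry can miss small-airway change, so pre-fire FEV1 is only a partial control for R5.
- **That section 3.2 is wholly cross-sectional.** It also plans prospective analyses of incident disease. The gap is in the survey comparisons.
- **That fitter crews took the heaviest exposure.** The protocol does not say how crews were deployed. The referents missed the fire mainly through annual leave, a reason not obviously tied to lung health. Selection by lung function is possible, not shown.
- **That the SE would fall by 20% to 56%.** That applies sqrt(1 - r²) to raw correlations of 0.6 to 0.9 and ignores the covariates already in the model.
- **That the spirometry is claimed to be unique.** In section 1.2 that word belongs to the exposure records: "Importantly, and uniquely, detailed records held by the LFB will provide an objective, semiquantitative estimate of professional exposure to fire smoke". The spirometry is added afterwards as a further strength.

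**Conclusion.** The point holds for the secondary FEV1 and FVC analyses. The protocol promotes pre-fire spirometry and seeks consent to obtain it, but its survey analysis names no use for it. Followed as written, the model gives less precise estimates that are more open to confounding than the available data allow.

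The gain in precision is uncertain: about 2% to 48% off the standard error for an assumed partial correlation of 0.2 to 0.857. The lower end is a real possibility, because the three-yearly testing interval, the unstated gap from fire to survey and differences between spirometers could all lower the correlation. The confounding argument does not need a high correlation, but adjustment reduces the problem and does not remove it.

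This is a worthwhile improvement to the stated model. It is not a flaw that invalidates the study, and the primary R5 analysis is largely unaffected.

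**What to change.** In section 3.2:

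1. In the secondary FEV1 and FVC regressions, add as covariates the last LFB value before 14 June 2017 and the time since it.
2. Tabulate pre-fire FEV1 and FVC by exposure level, including the unexposed referents, as a direct check on the assumed equal distribution of confounders.
3. Optionally, as supporting analyses, fit a mixed model of the serial LFB values by exposure level, and add pre-fire FEV1 as a sensitivity covariate for R5. Section 3.1 also seeks consent by post from those who do not attend the survey, so the serial model could include consenting non-attenders.
4. Handle missing pre-fire values by multiple imputation. A missing-value indicator can bias a non-randomised comparison.

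The cost is a few lines of analysis text and the linkage of records for which consent is already sought. There are two small downsides. LFB and survey spirometers may differ, which covariate adjustment tolerates better than raw differences, and the interval since the last pre-fire test will vary between firefighters, which is why it belongs in the model.
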